## 9.2 Sample size estimation:

In a previous study on using LNG for EC within 72 hours of UPSI (Glasier et al, 2010), the fraction of prevented pregnancies was 51.9% based on the Trussell's model. With the assumption that the fraction of prevented pregnancies in the placebo group is around 52%, and the fraction of prevented pregnancies in the treatment group should be at least 10% higher than that in the placebo group for it to be clinically meaningful, a minimum of 384 subjects in each group will be required to demonstrate superiority of the proposed treatment with a power of 80% and type I error of 0.05. Assuming that around 10% of the subjects may default follow-up, we plan to recruit a total of 860 subjects.

No interim analysis is planned as it is anticipated that co-administration of oral piroxicam with LNG will not adversely reduce its EC efficacy.

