UPA, another selective progesterone receptor modulator, has more recently been introduced as an oral EC. Two randomized controlled trials showed that UPA was as effective as LNG for EC within 72 hours of UPSI (Creinin et al, 2006; Glasier et al, 2010). When the results of the two RCTs were combined in a meta-analysis, UPA has significantly lower failure rate compared to LNG [1.36% (22/1617) vs 2.15% (35/1625),  $p=0.046$ ] (Glasier et al, 2010). The effectiveness of UPA as EC is maintained up to 120 hours after UPSI, which is currently the licensed indication of UPA. In contrast to LNG which has a limited administration period preceding the onset of the LH surge for it to be effective, it was demonstrated that a single dose of 30 mg UPA administered up till the time immediately before the LH peak could still significantly interfere with follicular rupture (Brache et al, 2010). It was initially postulated in some studies that UPA might also have some concurrent inhibitory effect on embryo implantation based on changes in some molecular and histological parameters induced by UPA, but this was not supported by subsequent in-vitro co-culture experiments. One study in Hong Kong also did not support a significant clinical effect of UPA as EC when administered post-ovulation (Li et al, 2016). Therefore, the journey in search of further improvement in the efficacy of oral EC methods, particularly one with effective post-ovulatory action, still continues.

Prostaglandins are “local hormones” that take part in a number of reproductive processes including ovulation (Duffy, 2015), fertilisation (Sugimoto et al, 2015), tubal function (Wanggren et al, 2006; Wanggren et al, 2008) and embryo implantation (Salleh, 2014). Hence, it is postulated that an inhibitor of the cyclo-oxygenase (COX) enzyme, the key enzyme involved in prostaglandin production, may potentially confer a “contraceptive”

effect and may act synergistically with LNG for EC, particularly to target at the post-ovulatory events in addition.

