### 4. Study design:

This will be a randomised placebo-controlled double-blind clinical trial. A dedicated research nurse will help coordinate subject recruitment, study administration and follow-up of subjects. Subjects who give written consent to participate in this study shall be randomised to either the piroxicam arm (Treatment group) or placebo arm (Placebo group) in 1:1 ratio according to a computer-generated randomisation list in blocks of 10 in sealed envelopes which are prepared by an independent person. The medication will be prepacked by an authorised third party not directly involved in this study. The subjects, clinicians and research staff will be blinded to the group assignment. The codes for the treatment groups will only be revealed to the investigators after completion of the whole study and statistical analyses. It is anticipated that subject recruitment shall take 20 months; follow-up of the subjects will be completed in 2 months further, and a summary of preliminary results will be available by 24 months.

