## 7. Study outcomes

### Primary outcome measure:

- Fraction of pregnancies prevented (%)  
[(expected pregnancies – observed pregnancies] / expected pregnancies]  
The number of expected pregnancies will be determined by the Trussell's model (Trussell J et al, Contraception 2003; 67:259-265)

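### The 80% power claim counts women where the primary outcome counts expected pregnancies; power for 52% against 62% prevented is nearer 7%

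*Combined protocol and SAP*

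**What the plan says.** Section 7 makes the fraction of pregnancies prevented the primary outcome: expected minus observed pregnancies, over expected pregnancies. It adds that "The number of expected pregnancies will be determined by the Trussell's model".

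Section 9.2 takes its control value from an earlier study of levonorgestrel (LNG) in which "the fraction of prevented pregnancies was 51.9% based on the Trussell's model". It assumes that "the fraction of prevented pregnancies in the placebo group is around 52" per cent, and that the fraction on piroxicam "should be at least 10% higher than that in the placebo group for it to be clinically meaningful". It then states that "a minimum of 384 subjects in each group will be required to demonstrate superiority of the proposed treatment with a power of 80" per cent and "type I error of 0.05". Allowing for about 10% lost to follow-up, the total is 860. Section 9.2 gives neither an expected pregnancy rate nor an expected number of pregnancies.

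The only pregnancy rates in the document are in section 2, which reports failures on ulipristal acetate and on LNG, pooled over two trials, as "1.36% (22/1617) vs 2.15% (35/1625").

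Section 9.1 compares the percentage of pregnancies prevented by a chi-square test, without naming the unit counted. It compares pregnancy rates, a secondary outcome, by Firth logistic regression.

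**The concern.** A sample size for two proportions needs a denominator made of units that can each succeed or fail. For the prevented fraction, that denominator is the set of pregnancies expected without treatment. It is a small part of the women enrolled. Section 9.2 uses all the women. That inflates the information in the trial by the inverse of the expected pregnancy rate.

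The primary hypothesis is therefore tested with far less power than stated. If piroxicam delivers exactly the gain that the protocol calls clinically meaningful, the trial will very probably miss it. With 80% power on record, a null result could be taken as evidence that piroxicam adds nothing. Conversely, a significant result would need an observed difference far larger than 10 points, so it would overstate a true effect of that size.

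**Working it through.** **Inputs**

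- Control and target prevented fractions, 52% and 62% (section 9.2).
- 80% power and alpha 0.05, sidedness not stated (section 9.2).
- Allocation "in 1:1 ratio according to a computer-generated randomisation list" (section 4).
- Observed pregnancy rate on LNG, 35/1625 = 2.15% (section 2).
- Prevented fraction in the cited LNG study, 51.9% (section 9.2).

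**Step 1. Reproduce 384.** With p1 = 0.52, p2 = 0.62 and mean p = 0.57, the pooled two-proportion formula is

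n = [1.96 × √(2p(1−p)) + 0.842 × √(p1(1−p1) + p2(1−p2))]² / (p2−p1)² = 383.57, rounded up to 384.

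The match is exact for a two-sided test without continuity correction. A one-sided test gives 303. Reading the 10% as relative (52% against 57.2%) gives 1,438. So the plan used an absolute 10 points, a two-sided test and women as the denominator. Allowing for loss to follow-up, 384/0.9 = 427 per group or 854 in total, consistent with 860.

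**Step 2. Expected pregnancies.** Observed rate = expected rate × (1 − prevented fraction), so

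expected rate = (35/1625) / (1 − 0.519) = 4.48%.

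Per group of 384:

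- expected: 384 × 4.48% = 17.2
- observed on placebo: 17.2 × 0.48 = 8.3 (2.15% of women)
- observed on piroxicam: 17.2 × 0.38 = 6.5 (1.70% of women)

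**Step 3. Power for 52% against 62%.** If the expected rate is the same in both arms, comparing prevented fractions amounts to comparing pregnancy counts. Enumerating two binomials with n = 384 and a two-sided 5% Pearson chi-square test gives the following. The expected rates other than 4.48% are assumptions, chosen to show sensitivity.

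| Expected rate | Expected pregnancies per group | Power at 384 per group | Women per group for 80% power |
|---|---|---|---|
| 3% | 11.5 | 5.5% | 22,209 |
| 4.48% | 17.2 | 6.7% | 14,783 |
| 5.5% | 21.1 | 7.6% | 11,982 |
| 8% | 30.7 | 9.1% | 8,147 |
| 10% | 38.4 | 10.1% | 6,459 |

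Other methods at 4.48% agree:

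- Fisher's exact test: about 4%.
- Poisson Wald test on the difference in prevented fraction: 6.5%.
- Two-proportion formula with 17 expected pregnancies as the denominator: 8.4%.
- One-sided test, normal approximation: 11.6%.
- All 430 randomised per group retained: 7.2%.

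The formula returns 80% at 384 per group only if the expected rate is set to 100%, that is, if every woman would have conceived.

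**Step 4. Precision.** Treating observed counts as Poisson and expected counts as fixed, the standard error of the difference in prevented fraction is √((0.48 + 0.38)/17.2) = 0.224. The 95% confidence interval is then the estimate ± 1.96 × 0.224, or about ±44 points, against a target of 10.

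**Step 5. Detectable effect.** With 384 per group and 52% prevented on placebo, about 80% power is reached when the piroxicam arm prevents about 96% (power 79% at 96%, 55% at 90%). Over the assumed 3% to 10% range, the required fraction runs from about 100% down to about 86%.

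**The case against.** The strongest objection is that 4.48% is derived. The 2.15% is pooled over two trials and the 51.9% is cited from one study, and the document does not show that they describe the same women. That is fair, and it is why the figures need ranges. It does not rescue the 80%: no expected rate between 3% and 10% gives power above about 10%.

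A second objection is that the power above is for a test on pregnancy counts per woman, while section 9.1 does not define how its chi-square test on the prevented fraction would be built. This also stands. The count-based test is a substitute that is valid when expected rates are balanced between arms, and the alternatives in Step 3 agree closely. The ambiguity carries its own risk. If the chi-square test follows section 9.2 and applies the prevented fraction to all women, it is not a valid test. A simulation with 52% prevented in both arms, 384 per group and a 4.48% expected rate rejects about 71% of the time at nominal 5%. This is conditional, because the plan does not state the unit.

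Third, Firth regression with profile-likelihood intervals is already planned and suits rare events. It reduces bias and reports uncertainty, but it adds no information to about 15 pregnancies in all.

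Finally, the plan does not say how a null result would be interpreted, so misreading one is a risk and not something the plan commits to.

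**Conclusion.** The concern holds. The arithmetic behind 384 is correct for its formula, but the unit of analysis is wrong for the primary outcome in section 7, and the 80% is unsupported. At the rate implied by the protocol's own figures, power is about 7%, roughly one twelfth of what is stated. If the true gain is 10 points, the trial would miss it about 93 times in 100.

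This rests on a two-sided test, an absolute 10-point difference, equal expected rates in the two arms and the derived 4.48%. Neither a one-sided test nor the Firth model brings power near 80%, and the relative reading of 10% implies a smaller effect still. This must be corrected, because the stated power governs how the primary result will be read.

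**What to change.** In section 9.2, withdraw the 80% figure and state what 860 women deliver:

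- About 17 expected pregnancies per group of 384, marked as derived from the 2.15% and 51.9% already cited.
- About 7% power for 52% against 62% prevented (5.5% to 10.1% for assumed expected rates of 3% to 10%).
- A detectable prevented fraction of about 96% at 80% power (about 86% to nearly 100% over the same range).

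State that the trial estimates the prevented fraction in each arm, and the ratio between arms, with confidence intervals. Add that a non-significant result will not be read as absence of a 10-point benefit. In section 9.1, name the unit and denominator of the primary chi-square test so that the error does not pass into the analysis.

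The cost is redrafting section 9.2, one new sentence on interpretation and a clarification in section 9.1. The stated power becomes far less favourable. No extra women, procedures or changes to enrolment are needed.

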## 10. Direct access to source data / documents:

Trial-related monitoring, audits and regulatory inspections are allowed.

## 11. Quality control and quality assurance

Not applicable

## 12. Ethics:

Ethics approval will be applied before commencement of study. The study medication has been licensed in Hong Kong as an analgesic. Side effects associated with a single oral dose of piroxicam is expected to be minimal. There should not be any major ethical concern. Clinical trial certificate shall be obtained from the Department of Health, Hong Kong, before the study is commenced.

The study will be conducted in compliance with the protocol of the International Conference on harmonization (ICH) Good Clinical Practice (GCP), as well as applicable local regulatory requirement(s) by the Institutional Review Board (IRB), The University of Hong Kong (HKU) / Hospital Authority Hong Kong West Cluster

(HA-HKWC). Confidentiality of the study subjects will be preserved in accordance to these protocols and regulations.

The patient information sheet will explain the aims of the study, possible adverse effects and confidentiality issues. Informed consent will be obtained before the subjects are recruited into this study. Participation in and withdrawal from the study is voluntary.

**13. Data Handling and record keeping**

All data will be stored and analysed using SPSS. All the investigators will be responsible for data management including data coding, monitoring and verification.

**14. Financing and insurance**

Funding will be supported by internal research fund of the Department of Obstetrics and Gynaecology, The University of Hong Kong

**15. Publication policy**

The findings of this study will be submitted for consideration for publication in peer-reviewed scientific journal.

**16. Supplements**

Nil
